4.2 SCIENTIFIC RATIONALE FOR STUDY DESIGN

Flint is naturally divided into 4 quadrants by the cross streets of Saginaw Street and 5th Avenue. The Stroke Ready community intervention will be sequentially delivered to each quadrant, eventually reaching the entire community. Quadrants will be randomly selected and then for 6 months the research team will focus on the selected quadrant of the city (Table 1). During this time the peer workshops will occur, flyers and posters distributed and workbooks made available. At the end of six months, the materials will remain in the quadrant but efforts will shift to the next quadrant. Delivery of the intervention in quadrants will: 1) allow more efficient use of resources; 2) optimize intervention efficacy by increasing the likelihood of repetitive exposure to the intervention and 3) allow for exploratory analyses to determine whether the hospital or community intervention is most important and clarify the efficacy of the overall intervention.

5 STUDY POPULATION

5.1 INCLUSION CRITERIA

Workshops will be open to the public. While our primary outcome will observe Flint-based stroke treatment rates, stroke preparedness is a global public health message applicable to most people; therefore, participants will not be excluded if they live outside the city limits. Similarly, the workshops are designed for English-speaking adults; however, non-English speaking people will not be excluded. In collaboration with community partners, Stroke Ready materials were carefully designed as to not be harmful to vulnerable populations, including women and

minorities, children, and the homeless population. The Stroke Ready workshop should not be harmful to children as it is adapted from material delivered to adults and youth in the pilot study (HUM00098718). Thus, if adults choose to bring their children, they will be accommodated in the workshops.

Inclusion of Women and Minorities: Given this is a community education intervention no one will be excluded from the community-level interventions. The Stroke Ready campaign should not be harmful to women or minorities.

Inclusion of Children: The Stroke Ready campaign should not be harmful to children as it is adapted from material delivered to youth in the pilot study (HUM00098718). Children will not be specifically recruited but they will be allowed to attend workshops if they are present.

Inclusion of Vulnerable Populations: Conscious efforts will be made to deliver the Stroke Ready intervention to vulnerable populations (e.g. homeless, cognitively impaired adults, college students, economically or educationally disadvantaged persons). Data will not be collected.

5.2 EXCLUSION CRITERIA

Given this is a community education intervention no one will be excluded from the community-level interventions. The Stroke Ready campaign should not be harmful to vulnerable populations.

5.3 STRATEGIES FOR RECRUITMENT AND RETENTION

The research team and Stroke Ready peer-leaders will work together to recruit organizations and participants for the Stroke Ready workshops through recruitment announcements, flyers, internet platforms, and word-of-mouth. Additionally, the research team or peer leaders may provide a courtesy reminder call several days before the workshop. Since Flint is naturally divided into 4 quadrants the study team will select each quadrant for implementation and then for about the next 6 months they will focus their workshop recruitment efforts and material dissemination on the selected quadrant of the city. However, given the commitment to CBPR the quadrant implementation is preferred but we would not forego a workshop in a quadrant that we are not focusing on at the time if requested. During this time the research team and community partners, including peer leaders, will work together to implement the Stroke Ready workshops and distribute educational posters and materials. At the end of about six months, the materials will remain in the quadrant and efforts will shift to the next quadrant for recruitment and workshop delivery.

To overcome challenges of recruiting racial minorities, low-income individuals, and other disadvantaged populations due to lack of transportation, childcare, inconvenient hours, etc., the research team designed the workshops such that participants can participate at their convenience. The workshops are voluntary and will be delivered by peer-leaders at locations during times that are convenient for the community (e.g. after church services, during lunch breaks). Additional factors that facilitate program recruitment and participation are: 1) the workshops, as well as all Stroke Ready materials and activities, are free and have no more than minimal risk; 2) recruitment materials and intervention components were created by the community for the community; 3) the research team has gained support of local leadership and

community members with strong ties in the Flint community; 4) children will be allowed to attend (HUM00098718).

Internet platforms will be utilized to recruit participants. Upcoming workshop events will be posted on the Stroke Ready Facebook page and website.

The research team will oversee the activities related to workshop participant recruitment to track the campaign's reach and resources, and workshop delivery processes to assess workshop fidelity.

5.4 PEER LEADERS

To build community capacity as well as to increase the uptake and relevance of the workshops in the community, peer leaders will be hired from the Flint community as much as possible for our community based intervention. We will recruit up to 16 peer leaders to start but recognize there may be turnover during the intervention or high demand for additional workshops; therefore, the research team may need to recruit additional peer leaders during the workshop delivery phase. We will pay about \$15 per hour for recruitment and delivering the workshops that include the minimum required attendees. We anticipate that some the peer leaders may be UM-Ann Arbor or UM-Flint students who prefer class credit to payment. If this were the case, we would work with the institution to facilitate credit attainment. Peer leaders will be cross-trained so that if one is unable to show up on the day of the workshop another peer leader will be able to facilitate the group. Peer leaders will be strongly encouraged to deliver workshops every week for the duration of the project.

The peer-leaders are not participants, but facilitators of the workshop. They will facilitate the workshop discussion and activities through use of a peer leader workshop facilitation guide and pre-recorded script. The research team will be available during business hours and as much as possible outside of business hours for any questions or concerns.

The peer leaders will be over the age of 18. There are no exclusions related to race/ethnicity or sex.

6 STUDY INTERVENTION(S) OR EXPERIMENTAL MANIPULATION(S)

6.1 FIDELITY

6.1.1 INTERVENTIONIST TRAINING AND TRACKING

The research team will conduct fidelity assessments and collect process measures to track any changes or adaptations made to a Stroke Ready workshop and Stroke Ready campaign upon implementation. Peer leaders will also be trained in and complete a self-fidelity checklist after each workshop to track and communicate field observations made during workshops, and to document any adaptations made for time constraints or settings. The Stroke Ready campaign will also collect primary, secondary and tertiary outcomes (Table 2).

Fidelity Assessment

The research team will randomly select a proportion of workshops to observe for fidelity assessments to assess whether the workshop is being conducted as intended. Other fidelity

measures the research team will collect include exposure of dose, quality of delivery, participant responsiveness, program differentiation, and intervention complexity.

Aspects of fidelity the research team will measure (See Appendix A) include:

Dose delivered – as measured by workshop duration and content delivered;

Dose received – as measured by post-intervention survey to determine exposure to all intended activities per workshop type & satisfaction;

Quality of delivery – as measured by facilitator's utilization of techniques prescribed by the program (use of facilitator's guide, use of audio/PowerPoint, appropriate facilitation of activities);

Reach – as measured by numbers served.

Barriers to participation--documented by peer leaders on the self-fidelity checklist, as well as by the research team during fidelity assessments;

Participant responsiveness – as measured by satisfaction survey to identify participant interest in activities and perceived usefulness of information;

Program differentiation – as measured through a satisfaction survey to identify which workshop components participants liked most;

Intervention complexity – as measured through tracking peer facilitator's attendance at initial training session and completion of refresher training if it has been longer than 6 months since the facilitator last delivered a workshop (which will be available as an online training module);

Context – as measured through observation field notes of aspects of environment that may influence intervention implementation or study outcomes.

Uptake of the Stroke Ready video and internet materials will be measured by counts of internet hits from internet protocol (IP) addresses of video viewers from within Flint. This will be tabulated by linking to a database that maps IP address to physical locations.

Table 4: Process Measures	
Community Intervention Process Measures	
Uptake: Music video	-Number of internet hits -Number of internet hits from within Flint
Uptake: Workshops	-Number of workshop locations -Number of workshops held (each type) -Number of workshop participants
Uptake: Print media	-Number of mailers, action plans and brochures distributed
Uptake: PSAs	-Number of plays of PSAs on radio and TV
Facebook uptake	- Number of likes on Facebook page
Instagram uptake	- Number of followers on Instagram page
Website uptake	-Number of hits to Stroke Ready website

	- Number of hits to Stroke Ready website (from within Flint via IP address)
Uptake: Workbook	-Number of materials distributed
Community Satisfaction	-Workshop survey -FASt Survey -Speak to Your Health Survey

6.2 ENDPOINT AND OTHER NON-SAFETY ASSESSMENTS

The primary outcome will be measured from hospital electronic record (EMR), billing data and/or from the Get With the Guidelines (GWTG) stroke registry data. Data will be separately received from the three hospitals in Flint where patients are sent for EVT (received letters of support and UFA in progress), which together account for 95% of all stroke treatments in Flint residents. The study population will be patients with a primary diagnosis of ischemic stroke using ICD-9 codes and/ or ICD-10 codes^{33, 34}. The primary outcome will be any thrombolysis which includes both IV tPA (MS-DRG 61-63 or ICD-9 procedure code 99.10), intra-artery treatment (MS-DRG 21-23 or CPT codes 37184-6, 37201, 75896) and the combination identified by ICD-9 and ICD-10 codes.³ The research team will attempt to obtain data from 2010 to 2021 if available to account for linear trends (about 6000 ischemic stroke and 8000 total strokes and TIAs). Data will also be obtained from the de-identified publicly available Michigan State Inpatient Database for stroke rates in comparator cities.

Secondary Outcomes: The community secondary outcomes are the number of stroke patients who arrive by ambulance and IV acute stroke treatment rates. Data will be obtained from the EMR. We also request data from the State of Michigan, specifically Michigan Department of Health and Human Services, Michigan EMS Information System UFA (21-UFA04001) or GWTG data of the three hospitals in Flint.

Tertiary/exploratory outcomes: The tertiary/exploratory outcomes include onset to door time and door to needle time which will be obtained from the hospital EMR and GWTG. Survey data will also be obtained. The community survey, Speak to Your Health, is a biennial, geo-coded survey that has been designed and administered by the Flint community, Genesee County Health Department since 2003.³⁵ We added questions from the Stroke Ready pilot (HUM00098718) (including stroke attitude, self-efficacy, social norms, and written stroke preparedness vignettes) to this community survey (see Appendix B) that was administered in 2015/2017 and will continue in 2019 and possibly 2021. The research team may add stroke education exposure questions to the 2019 and 2021 STYH surveys (see section 29 of IRB application- exposure questions). These additions, along with the original questions, will assess community level change in response to the Stroke Ready program; as well as exposure to local stroke education (See Appendix B). Additionally, these same questions will be added to the Flint Area Study. This is a face to face interview of Flint residents. The survey data will be de-identified. STYH and FASt surveys are ongoing surveys in Flint. The data is de-identified and publically available.

7 STATISTICAL CONSIDERATIONS

7.1 STATISTICAL HYPOTHESES

- **Primary Endpoint(s):** The primary endpoint is change in acute stroke treatment rates (IV tPA and endovascular treatment).

- Secondary Endpoint(s): The secondary endpoints are change in acute stroke treatment rates (IV tPA) and ambulance utilization.

7.1.1 ANALYSIS OF THE PRIMARY ENDPOINT(S)

The primary analysis will be an interrupted time series comparison of acute stroke treatment rates in the three Flint hospitals. The pre-intervention period will be defined using EMR data prior to the start of the roll out of the community intervention. All patients admitted with a primary diagnosis of ischemic stroke in both the pre-intervention and intervention periods will be included in the primary analysis. Note: process measures evaluating the Stroke Ready campaign (quadrant crossover or music video view IP address) will not be linked to any obtained PHI. Logistic regression will be used to estimate the overall intervention efficacy (indicator variable) in a model predicting receipt of acute stroke treatment (binary variable). If a temporal trend exists in the pre-intervention period, we will adjust for the month since the start of the pre-period as a fixed effect while accounting for clustering at the hospital level. To maximize statistical power, both interventions (hospital-HUM00112536 and all community quadrants-this current protocol) will be parameterized with a single variable. With this approach, statistical power for the primary analysis will be more than adequate. Using hospital administrative and Medicare data, we estimate that at least 480 strokes per year will occur at the 3 Flint hospitals for a total of at least 1,440 strokes in the pre period and 1,800 in the post-period, but to be conservative we are requesting data from 2010 to 2021 about 8000 patients with a stroke. Assuming a doubling in treatment rates (pre-intervention Medicare treatment rate 2.2%),³⁷ we will have over 90% power to detect this difference considering a two-sample binomial difference in proportions. This estimate is consistent with prior simulation work based on ARIMA analyses (effect size of 1.0 (pre-intervention monthly treatment rate = 2.2%, standard deviation = 2.1, predicted post-intervention treatment rate 4.3%, auto-correlation=0.3).³⁸

7.1.2 SECONDARY ANALYSES: REGIONAL COMPARISONS AND QUADRANT-BASED ANALYSES TO ENHANCE CAUSAL INFERENCE

Secondary analyses will explore the extent that such confounding may influence the primary analysis and enhance the ability to draw causal inferences from the primary analysis. First, we will repeat the primary analysis with a concurrent control group consisting of other large Michigan metropolitan regions (regional control model) where African-Americans make up more than 25% of the population (Detroit, Saginaw, Muskegon, Benton Harbor). This analysis will control for regional effects that may lead to increased treatment rates that occur simultaneously with our intervention in Flint using data from the Michigan State Inpatient Database (SID),³⁹ which collects de-identified data on all acute care hospitalizations in the state of Michigan within a given year. Second, by delivering the intervention sequentially to geographic quadrants within Flint, we will explore whether increases in acute treatment rates parallel the geographic pattern of intervention roll out (geographic model). Specifically, each stroke patient in Flint will be geocoded to one of the four intervention quadrants using EMR data and a geocoding interface. Our primary analysis will then be repeated by modifying the intervention indicator variable to represent whether the intervention was active in the patient's geographic quadrant at the time of intervention.

7.1.3 EXPLORATORY ANALYSES: EFFICACY OF PROGRAM COMPONENTS AND TEMPORAL PATTERNS TO INFORM FUTURE INTERVENTIONS

To inform future interventions, will also perform a series of hypothesis-generating analyses to inform which elements of the program were most effective and the temporal properties of the program. Due to power concerns, our primary analysis does not consider the difference between the hospital and community effects. Thus, we will first estimate the proportion of the change in the acute stroke treatment rate attributable to the hospital-based intervention vs. the community-based intervention by repeating our geographic model including an indicator variable representing the time period of the hospital intervention as well as a community interaction term. In this way, we will be able to explore whether the Stroke Ready hospital or community based intervention was the most efficacious and whether there was synergy between the interventions. The stepped wedge design is a key innovation to this end. In typical multi-level interventions when all of the elements are rolled out nearly simultaneously, it is impossible to estimate which elements have the highest leverage, however with the stepped wedge design it is possible to gain a greater understanding of which elements are most important. Using simulation analyses, we estimate that there will be 70% power to find a doubling at the community level, 55% power to find a doubling at the hospital level and 21% power to find a doubling through a community-hospital interaction. Because this power is inadequate for a hypothesis-testing evaluation, we have specified this analysis as an exploratory analysis whose purpose is enhance our understanding of the importance of intervention elements and to inform future interventions. Second, we will determine the temporal properties of the Stroke Ready intervention by adding a linear slope term and exploring quadratic terms in our geographic model to estimate the time delay between intervention and changes in treatment rates and whether treatment rates level off or decline as the intervention persists into its latter years. Finally, a strength of our data collection approach is that we will be able to inexpensively assess the sustainability of intervention effect using Michigan SID data years after the intervention is completed without needing to perform additional data collection. Together, such analyses will determine the sustainability of the intervention and inform future interventions.

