Print media	Posters, brochures	self-efficacy, attitude, knowledge	Churches, organizations, businesses	Peer Leaders, research team, social media, website
Public Service Announcement	Educational PSA of stroke preparedness	self-efficacy, attitude, social norms, knowledge	Flint community	Radio
Website, Facebook, Instagram	Dissemination of information, education, and materials	self-efficacy, attitude, social norms, knowledge	Flint community	Internet
Mailers: magnet, brochure, information letter, action plan	Dissemination of information and education, and materials	self-efficacy, attitude, social norms, knowledge	Flint community	United States Postal Service

We have submitted the near final version of the Stroke Ready materials. Any further changes in the materials will not change the content. Additionally, graphics may be slightly altered to

enhance the professional, finished look of the product. None of the content of the materials should significantly change after IRB approval.

We reviewed the content, graphics, and music with the community to assure appropriateness of content and cultural sensitivity. No participant is forced to watch or read any of the materials. They are provided to the community for them to use as they wish.

Component 1: Peer-led workshop

Peer leaders will deliver the Stroke Ready workshop. It is expected that about 300 workshops will be delivered throughout the 6-month time period per quadrant (x 4 quadrants). The workshops vary in length from (60, 30, 15, 5 minutes), whether they are peer-led and the amount of interactive activities. For all materials and activities, if issues arise e.g., time constraints, the peer-leader may exclude some portions or alter formatting/order of certain sections in the workshop. These changes may be required in response to participant feedback or time constraints. As community organizations have moved to conducting their meetings via virtual format (eg. Zoom, BlueJeans, etc.) during the COVID-19 pandemic, workshops will be delivered via virtual format to maintain social distancing requirements. Community organizations hosting the workshop during their regularly scheduled meetings will provide the peer educator with the meeting link. All aspects of the workshops will remain the same and no data will be collected or saved from participants.

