8 DATA CONSIDERATIONS

8.1 DATA

Data and information collection from workshop participants will cease pending the approval of the IRB Amendment (Ame00084323). Previously collected satisfaction surveys and address forms (June 2018-January 2019) will be stored securely and analyzed. Pending amendment approval, there will be no data or information collected from workshop participants (no satisfaction surveys or address forms).

The only PHI identifiable data in this study will be addresses and hospital dates of stroke patients collected from the three Flint area hospital detailed below.

De-Identified

The community surveys, Speak to Your Health and the Flint Area Study, are publically available and de-identified. The Michigan State Inpatient Database (SID), which collects data on all acute care hospitalizations in the state of Michigan within a given year is also de-identified. The satisfaction survey and fidelity assessments will not include personal identifiers.

Identified

A process measure is the number of views of the Stroke Ready music video. This will be assessed by the number of internet hits from the Flint community via internet protocol (IP) addresses. The only use of this data is to assess the whether or not the video was viewed by and for the community it was intended. Additionally, basic analytics will be used to assess website visits. Data extracted will be number of views on the Stroke Ready website—total visits and visits from the Flint community via IP addresses. Exploratory analytics may include new versus returning users, frequency and engagement of site visits. We request a waiver of informed consent.

Hospital data will be obtained from the Flint area hospitals. Data may include basic demographics, treatments, date of admission and date of treatment, stroke process measures, comorbidities, and outcomes of stroke patients. This data will include identifiable information in the form of addresses, in order to map the stroke event, as well as dates. We expect some of this data to come from the EMR, billing records and Get With the Guidelines Stroke. We are working with each hospital to establish a data use agreement. We request a HIPAA authorization waiver and a waiver of informed consent.

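### Section 7 makes no provision for the pandemic months, which may be about half of the post-launch period, so part of any COVID-19 shift enters the intervention estimate

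*Combined protocol and SAP*

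**What the plan says.** - **Primary model (Section 7.1.1).** "The primary analysis will be an interrupted time series comparison of acute stroke treatment rates in the three Flint hospitals". It is a logistic regression of receipt of treatment on an intervention indicator: "both interventions (hospital-HUM00112536 and all community quadrants-this current protocol) will be parameterized with a single variable". Month enters as a linear term only if the pre-period shows a trend.
- **Pre/post split (Section 7.1.1).** "The pre-intervention period will be defined using EMR data prior to the start of the roll out of the community intervention".
- **Data window (Section 6.2; also Table 2).** "The research team will attempt to obtain data from 2010 to 2021 if available to account for linear trends".
- **Ambulance arrival (Section 7.1.4).** Logistic regression with an intervention-period indicator; no trend term is mentioned. IV tPA is analysed as an interrupted time series.
- **COVID-19.** It appears for delivery only. Section 4.1, Component 1, says that "workshops will be delivered via virtual format to maintain social distancing requirements", and the version 4.1 entry in Section 9 covers that change alone. Section 7 has no pandemic term, no exclusion of pandemic months and no pre-pandemic sensitivity analysis.
- **Launch date.** None is stated. The nearest evidence is in Section 8.1: "Previously collected satisfaction surveys and address forms (June 2018-January 2019) will be stored securely and analyzed".

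**The concern.** A before/after indicator credits to the intervention whatever else changed after launch. If care-seeking, ambulance use or case mix shifted during the pandemic, and many post-launch months are pandemic months, the coefficient mixes that shift with the effect of Stroke Ready. A linear month term whose use depends on the pre-period cannot represent a step in 2020. The primary treatment estimate and, more so, the ambulance result could move in either direction for reasons unrelated to the programme. Without a pre-specified analysis, handling of these months would be decided after the data are seen.

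**Working it through.** **Plan's own figure.** 1,440 pre-period and 1,800 post-period strokes, 2.2% against 4.4%, pooled two-proportion test, two-sided 0.05 (alpha is not stated, so assumed): power 93.6%. The plan's claim of more than 90% reproduces. The doubling is an odds ratio (OR) of (0.044/0.956)/(0.022/0.978) = 2.05.

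**Share of post-launch months in the pandemic.** Assumptions: launch June 2018 (proxy from Section 8.1), data to December 2021, pandemic from March 2020 (the documents give no date).
- June 2018 to December 2021 = 43 months; March 2020 to December 2021 = 22 months; 22/43 = 51%.
- Cross-check from the plan's post-period size: 1,800/480 = 3.75 years = 45 months; 22/45 = 49%.
- Other dates: launch January 2017, 22/60 = 37%; launch January 2019, 22/36 = 61%; data ending December 2020, 10/31 = 32%.

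**Share of a pandemic step carried by the indicator** (projection of a pandemic indicator on the planned model terms):
- no month term: 22/43 = 51%;
- month term, data from January 2010: 33%;
- month term, 36-month pre-period: -36%, so the bias changes sign.

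**Treatment, no true effect, no month, data from 2010.** 480 strokes per year = 40 per month; pre 101 × 40 = 4,040, post 43 × 40 = 1,720. Hospital clustering is ignored. The pandemic OR range of 0.7-1.25 is an assumption.
- OR 0.7: baseline odds 0.022/0.978 = 0.0225; pandemic odds 0.0157, rate 1.55%. Post rate = (21 × 2.2 + 22 × 1.55)/43 = 1.87%. Fitted OR = 0.0190/0.0225 = 0.85.
- Variance of the log OR = 1/(4,040 × 0.022 × 0.978) + 1/(1,720 × 0.0187 × 0.9813) = 0.0115 + 0.0317; SE 0.208. z = ln(0.846)/0.208 = -0.80; chance of p < 0.05 = 13%.
- OR 1.25: pandemic rate 2.74%, post rate 2.47%, fitted OR 1.13; false-signal rate 10%.
- With month (logistic fit to expected counts): fitted OR 0.89-1.08; false-signal rate about 6%.
- With month and a 36-month pre-period, a pandemic OR of 0.7 gives 1.13.

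**Treatment, true doubling, no month.** A pandemic OR of 0.7 moves the fitted OR from 2.05 to 1.73.

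**Ambulance arrival, indicator only, 50% baseline (assumed), data from 2010.**
- OR 0.7: pandemic rate 41.2%, post rate (21 × 50 + 22 × 41.2)/43 = 45.5%, fitted OR 0.83. SE = √(1/(4,040 × 0.25) + 1/(1,720 × 0.248)) = 0.058; z = -3.14; false-signal rate 88%.
- OR 1.25: pandemic rate 55.6%, post rate 52.8%, fitted OR 1.12; z = 1.97; false-signal rate 51%.
- With only 1,440 pre-period strokes the SE is √(1/(1,440 × 0.25) + 1/(1,720 × 0.248)) = 0.072, and the false-signal rates fall to 72% and 36%.

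**Geographic model.** Six-month steps from June 2018 bring in quadrants in June 2018, December 2018, June 2019 and December 2019. No quadrant is then unexposed in any pandemic month, so this model cannot separate the two unless roll-out slipped.

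**Cost of adding a pandemic term** (power for a doubling, same logistic fits):

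| Pre-period | Month term | Without pandemic term | With pandemic term |
|---|---|---|---|
| From 2010 | no | 99% | 95% |
| From 2010 | yes | 68% | 67% |
| 36 months | no | about 92% | 83% |
| 36 months | yes | 45% | 37% |

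**Partial roll-out.** Of the 21 post-launch months before March 2020, 18 (June 2018 to November 2019) precede the fourth quadrant. If the effect scales with quadrants reached (assumed), with a full-exposure OR of 2.05 and no pandemic effect, adding the term with data from 2010 moves the fitted OR from 1.79 to 1.53 and power from 94% to 49% without month. With month it moves from 1.61 to 1.50, and power from 36% to 25%.

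**The case against.** **The plan already has a safeguard.** The regional control model in Section 7.1.2 is meant for changes that coincide with the intervention, and a pandemic effect shared by Michigan cities is one. This stands in part: it could remove a shared effect on treatment rates. It is secondary, however, it is not described as handling COVID-19, and it is not specified for ambulance arrival.

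**A reader might infer that this safeguard fails because Flint and the comparator cities are measured differently.** Section 6.2 names the "Michigan State Inpatient Database for stroke rates in comparator cities". But Table 2 lists that database together with the Flint hospitals as the primary outcome's source, and Section 7.1.2 says that it "collects de-identified data on all acute care hospitalizations in the state of Michigan". Flint may therefore already come from it in that model. Even if not, a difference in ascertainment that stays constant over time would be absorbed by a city term, and nothing shows a change at launch. The documents do not support this reading.

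**The primary endpoint moves little.** An OR of 0.85-1.13 is small beside the planned 2.05, and a 6-13% false-signal rate is a modest rise from 5%. This stands. The larger exposure is ambulance arrival, and that rests on an assumed 50% rate.

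**The remedy can remove real effect.** This also stands. Because most pre-March-2020 months are partial roll-out, later growth in a true effect would be credited to the pandemic. It argues against putting the term in the primary model.

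**The dates are inferred.** True. If the post-period were only the 24-month roll-out from June 2018, the share would be 3/24 = 12.5%. The 3.75 years implied by 1,800 strokes and the data window to 2021 point to the longer period.

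**Conclusion.** The gap is real and moderate. The current plan adapts delivery to COVID-19 but not the analysis, and the single intervention coefficient takes up part of any pandemic shift in the outcomes.

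For treatment the distortion is small to moderate. For ambulance arrival, which has only an indicator, it could produce a false conclusion. These sizes rest on an inferred June 2018 launch, a March 2020 start, data to December 2021 and an assumed pandemic OR; the documents give no size or direction for a pandemic effect.

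Two stronger readings are not supported. One is that the indicator takes up the whole pandemic effect: even without month it carries about half, and with month the share is smaller or reversed. The other is that a pandemic term costs about one point of power whatever the model: that holds only with month included and data from 2010.

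**What to change.** Keep the primary model as written. Pre-specify two sensitivity analyses for the treatment endpoints (any treatment, and IV tPA) and for ambulance arrival:

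1. Add an indicator for admissions from March 2020.
2. End the series at February 2020.

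State that a conclusion that changes under either analysis cannot be attributed to Stroke Ready alone. Also state the launch date and the end of the post-period, on which the size of the problem depends.

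**Cost.** Some SAP wording and two extra fits, with no new data. The price is in interpretation: both analyses are less precise, as the table shows, and on the planned six-month steps both lean on partial roll-out and may understate the full-exposure effect. The SAP should say so, so that a weaker result there is not read as proof of no effect.
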